Title: Evaluation of pain alleviating strategies during allergy shots (Subcutaneous immunotherapy): A randomized controlled study (Pain Perception with Allergy Shot Techniques: PPAST)

Principal Investigator

- [name] MSN, APRN, PCNS-BC, CPEN

Co-Investigators

- [name] [name], CPN
- [name] [name], AE-C
- [name] [name], CPN
- [name] [name]
- [name] [name], CPN
- [name] [name], CPN
- [name] [name], CPN
- [name] [name]
- [name] MD
-

Research Coordinators

- [name], BSH
- [name], BSN, RN, CCRC
- [name], BSN, RN, CCRC

Project Consultant / Data Analyst

- [name] MSN, ARNP, PCNS-BC, FNP-BC

Rationale and Purpose

Subcutaneous Immunotherapy (allergy injections) is a potentially disease-modifying therapy that is effective for the treatment of allergic rhinitis/conjunctivitis, allergic asthma and stinging insect hypersensitivity. Pain, which results from the irritation of nearby nerves is a common concern of patients, particularly in children, during or after the injections. This can be a stressful and negative experience for the children. There are various techniques available to minimize pain in general. However, there is a lack of published research on how to use these techniques in children receiving allergy injections. The purpose of this study is to evaluate and compare the efficacy of the standard of care method (Ethyl Chloride/Pain Ease Spray) and three non-pharmacological pain control devices (Buzzy Bee I, Buzzy Bee II and Shot Blocker) in decreasing the perception of pain during subcutaneous allergy injection in a pediatric allergy/immunology clinic setting.

Objective

- Evaluate and compare the effectiveness of utilizing various techniques to reduce the perception of pain during subcutaneous allergy injections in children

Possible Risks and Benefits

Risk Assessment

- The risks associated with study participation are consistent with standard of care risks. Potential risk for the study participants may be possible allergic reaction/skin irritation from the cold spray or ice pack or an increased level of anxiety.

Benefits Assessment

- The potential benefit associated with this research study includes a better understanding of study participant's response to their assigned distraction technique. This study may help identify which technique is more beneficial to use in children receiving subcutaneous immunotherapy to decrease the perception of pain and reduce anxiety related to immunotherapy treatment.

Study Design and Duration

This is a randomized controlled study. Approximately 100 children, age 4 – 17 years, who are currently receiving subcutaneous immunotherapy, will randomly select a blinded envelope which assigns the distraction technique to be utilized during their study participation. There will be 25 envelopes assigned to each study group for a total of 100 envelopes. Each envelope will contain a paper with a colored sticker for the associated group assignment and number sequence.

The distribution of group assignment by number sequence and color is as follows:

- Interventional Groups
 1. Shot Blocker® # 1-25 (RED)
 2. Buzzy I (vibrating only) # 26-50 (GREEN)
 3. Buzzy II (vibrating and ice wings) # 51-75 (BLUE)
- Control Group
 4. Ethyl Chloride/Pain Ease Spray # 76-100 (YELLOW)

The three interventional groups are currently marketed distraction devices. The control group is the current clinical standard of care option for pre-allergy injection application.

The study consists of two visits. Both visits will be conducted during the participants routine clinic visit for allergy injections. At the first visit the investigator will assess eligibility. An overview of the study requirements will be provided to parent/child and consent/assent will be obtained.

During the second visit, the child will be randomized to a distraction technique or standard of care group to be utilized with the allergy injection(s) administered at this visit. Adherence with institutional allergy injection guidelines will be maintained. Prior to the application of the distraction method, the investigator will interview the parent to collect data related to demographic information and their child's current allergy health and treatment regime. The child's pain perception will be assessed before and after the allergy injection. The parent's perception of their child's pain will be assessed after the allergy injection. The investigator will provide information on the application of the randomized method and will provide instruction on the completion of the pain scales and questionnaires. The investigator and study staff will not indicate a method preference or guide the child or parent with their pain level responses. After completion of the second visit, the child's study participation is complete.

Inclusion & Exclusion Criteria

Inclusion Criteria

- Children aged 4-17 years on injection immunotherapy
- A minimum of three allergy injection injections prior to enrollment at Visit 1

- Child accompanied by parent or legal guardian

Exclusion Criteria

- Children with a known pain or sensory disorders
- Developmental delays lacking necessary cognitive ability
- Administration of any form of pain analgesic within eight hours of randomization at Visit 2

Study Procedures

Visit 1:

Children aged 4-17 years who present to receive their injection(s) in the allergy clinic will be screened by the Principal Investigator or Co-Investigator for study inclusion and exclusion criteria. During their routine post-allergy injection 30-minute wait time, the investigator and the research coordinator will provide the parent and child with an overview of the study design, the risk and benefits assessment and study requirements. The investigator will advise the parent/child of the pain analgesic administration exclusion for the randomization visit. After obtaining parental permission and child assent, the child will be considered enrolled in the study. A subject ID will be assigned. A visible mark placed on the child's allergy injection chart will indicate the child is ready to be randomized at their next routine allergy injection visit.

Visit 2:

At a future allergy injection clinic visit the parent and the child will be asked if the child took any pain-relieving medicines, like Tylenol or Advil, within eight hours before coming to the clinic. If the participant needed this kind of medicine, the allergy shot appointment will be the same as before the study.

Study visit 2 will be completed at another routine allergy shot appointment. Preferably the next scheduled allergy injection visit.

If the participant did **not** take any pain relieving medicine within the previous eight hours, visit 2 will continue. The participants study group assignment will be determined. The envelopes identifying the four group assignments will be coded by number and color. The child will be presented with a basket containing all the envelopes. The investigator will instruct the child to select one envelope from the basket. The envelope selected at random by the child will determine the distraction method to be utilized prior to the allergy injection(s). The possible group assignments, one of three currently marketed distraction devices or the control group utilizing the current standard of care option, are listed below and are further detailed in Attachments I – III.

The four study groups are:

- Interventional Groups
 1. Shot Blocker®
 2. Buzzy I (*with ice pack-wings*)
 3. Buzzy II (*without ice pack-wings*)
- Control Group
 4. Ethyl Chloride/Pain Ease Spray

Before applying the assigned distraction method:

- Prior to randomization, the investigator will interview the parent to obtain the information needed to complete the Parent Demographic-Health-Treatment Questionnaire (Attachment V). The investigator will review the responses for any indicator of study ineligibility, ie, analgesic medication window.
- The investigator or study staff will review the Wong-Baker FACES Pain Rating Scale with the child. The child will be given a Wong-Baker FACES Pain Rating Scale form and asked to circle the face which most closely matches their current level of pain awareness prior to any intervention. (Attachment IV-a)
- The investigator or study staff will review the Numeric Pain Rating Scale (Attachment IV-b) with the parent. The parent will be instructed to circle the number on the scale which most closely matches their perception of their child's pain level immediately after receiving the allergy injection.

Application of the distraction method and administration of the allergy injection:

- The investigator will apply the assigned distraction method per method specifications to the injection site area (subcutaneous region of the back of the upper arm).
- The investigator will administer the subcutaneous allergy injection(s) within the time frame specified for the assigned distraction device utilized or per the standard of care guidelines for the Pain Ease Spray, as appropriate. If the child's treatment plan includes more than one injection, the assigned group technique will be utilized for all injections at the visit.

Post allergy injection procedures:

- Immediately following the allergy injection, the child will be provided with a second Wong-Baker FACES Pain Rating Scale form and be asked to circle the face which most closely matches their post-injection level of pain awareness.
- Immediately following the allergy injection, the parent will be reminded to circle the number on the Numeric Pain Rating Scale which most closely matches their perception of the child's post-injection pain level.
- The participant and parent will then complete the routine 30 minute wait time for post allergy injections.

Study participation is complete at the end of Visit 2.

Prohibited Medications

Analgesic medications administered within eight hours of Visit 2 are prohibited.

Adverse Event (AE)

An AE is any unfavorable and unintended sign, symptom temporally associated with the use of the study technique and does not imply judgment about causality.

AE's associated with the randomized intervention will be collected at Visit 2. The AE's relationship to the distraction technique will be assessed using the following guidelines for causality and grading severity. AE's related to the allergy injection will not be captured in this study.

AE Relationship to Study Distraction Technique Guide

Relationship to Study Distraction Technique	Comment
Definitely	An event that follows a reasonable temporal sequence from administration of the study distraction technique; that follows a known or expected response pattern to the suspected study distraction technique; that is confirmed by stopping the use of the study distraction technique; and this is not explained by any other reasonable hypothesis.
Probably	An event that follows a reasonable temporal sequence from administration of the study distraction technique; that follows a known or expected response pattern to the suspected study technique; that is confirmed by stopping the use of the study distraction technique; and that is unlikely to be explained by the known characteristics of the subject's clinical state or by other interventions.
Possibly	An event that follows a reasonable temporal sequence from administration of the study distraction technique; that follows a known or expected response pattern to that suspected study distraction technique; but that could readily have been produced by a number of other factors.
Unrelated	An event that can be determined with certainty to have no relationship to the study distraction technique.

AE Severity Grading

Severity (Toxicity Grade)	Description
Mild (1)	Mild; asymptomatic or mild symptoms; clinical or diagnostic observations only; intervention not indicated
Moderate (2)	Moderate; minimal, local or noninvasive intervention indicated; limiting age-appropriate Instrumental activities of daily living (e.g., preparing meals, using the telephone, managing money)
Severe (3)	Severe or medically significant but not immediately life threatening; hospitalization or prolongation of hospitalization indicated; disabling; limiting self-care activities of daily living (e.g., bathing, dressing, feeding self, using toilet, taking medications)

Discontinuation and Replacement of study participants

A child has the right to withdraw from study participation prior to the completion of Visit 2. Early withdrawal participants will be replaced one to one.

Participant ID assignment

The study participants will receive a Participant ID at Visit 1 which will be used for all data collection. The Participant ID used will range from 001 to 100. If a study participant withdraws before the completion of Visit 2, the Participant and associated group assignment will be replaced. Replacement Participant ID's will be sequential beginning with the number 101.

Data Collection

Medication administration data collected will be limited to the participant's current immunotherapy vial and dosing, distraction method utilized, site of the application method and, if applicable, antihistamine use and pain medication use. Demographic data collected will be age, race and gender. Symptom and health data point collection will target allergy injection reactions and the presence of allergic rhinitis, asthma and atopic dermatitis. (Refer to Attachment V). Pain perception data will be collected from both the child and parent using facial and numeric pain scales (Refer to Attachment IV).

All data collected will be entered into an EXCEL data collection tool and stored on password protected, secure computers. The data will accessible only to the investigators and research coordinators in the study.

Data Analysis

Quantitative component data collected and evaluated for this study will include the number of patient participants within the allergy department, randomized interventions used, diagnoses including allergic rhinitis, asthma and atopic dermatitis, immunotherapy medication and dose, antihistamine and pain medication utilization, patient and parental pain scores, adverse reactions, age, race, and gender.

Quantitative component data collected for this study will be extracted into Microsoft Excel spreadsheets and analyzed using Excel functions. Target population demographic characteristics will be analyzed using descriptive statistics by the principal investigator with the level of significance set at <0.05.

All information collected as part of evaluating the impact of this study will be aggregated data from the project participants and will not include any potential patient identifiers. Participant confidentiality will be assured by coding the participants using individual identification numbers for any analysis activities occurring outside of the electronic health record. This information will be stored in accordance with Nemours IRB policies and procedures. The Excel files containing codified data without protected health information (PHI) will be stored in password protected files at Nemours, on a password protected desktop computer in a locked office space accessible only by the principal investigator and study designees. The risk to patients participating in this project will be no different from the risks of patients receiving standard care.

Informed Consent Process

- Children who meet study criteria will be identified by Principal Investigator or Co-Investigator in the allergy clinic.
- Parents/guardians and child will be given an overview of the study, participation requirements, and complete information on being a voluntary participant in a research study. They will be given an opportunity to read the consent form, have questions answered and decide if they want their child to participate.
- If both the parent and child are interested in participating in the study, one parent/legal guardian will be asked to sign a Parental Permission and Consent Form.
- Children between the ages of 7 and 17 who verbalize understanding and are agreeable to the Assent information and study expectations will be asked to sign a Child Assent or Adolescent Assent Form.
- The Principal Investigator, Co-Investigator or Research Coordinator obtaining consent will witness the parent and child signatures, will sign both documents and provide copies of the signed consent/assent to the parent and child.

Participating Sites

The study will be conducted at Nemours Children's Specialty Care in the pediatric allergy clinics locations:

- Jacksonville Downtown
- Jacksonville South
- Fleming Island

Literature Cited

Angela Li, Zorash Montaño, Vincent J Chen, and Jeffrey I Gold :Virtual reality and pain management: current trends and future Directions:; *Pain Manag.* 2011 March ; 1(2): 147–157

[Rasha Srouji](#), [Savithiri Ratnapalan](#), and [Suzan Schneeweiss](#):Pain in Children: Assessment and Nonpharmacological Management.. *International Journal of Pediatrics*; Volume 2010

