ShotBlocker is a novel application of the gate control theory of pain management. ShotBlocker is a flexible plastic disk that has a number of blunt contact points on its underside. When pressed firmly against the patient's skin at the injection site, ShotBlocker saturates the sensory signals distracting the patient from the pain signals caused by the needle poke.

How to Use

1. Select the injection site and prep the skin as usual.
2. Hold ShotBlocker so that the blunt contact points touch the patient's skin at the injection site.
3. Press ShotBlocker FIRMLY against the skin. (A)
DO NOT MOVE OR REMOVE SHOTBLOCKER UNTIL THE INJECTION HAS BEEN COMPLETED.
4. Immediately administer the injection in the usual manner through or near the central opening of ShotBlocker. For subcutaneous injections, angle the needle as needed to give the injection. (B)
IF MORE THAN 20 SECONDS ELAPSE BETWEEN THE PLACEMENT OF SHOTBLOCKER AND THE INJECTION, COMPLETELY REMOVE SHOTBLOCKER FROM THE SKIN. REPEAT THE PROCESS BEGINNING WITH STEP 2.
5. After you have completed the injection and withdrawn the needle, remove and discard ShotBlocker.

U.S. Patent #6,902,554
© 2012 Bionix Medical Technologies.

[name]
[contact] • [contact]
www.BionixMed.com

II – Buzzy Bee I (*with ice pack-wings*) and Buzzy Bee II (*without ice pack-wings*)

Developed by a physician, Buzzy® is a reusable device for minor aches and pains.

Buzzy® is a personal consumer use product intended to be used by a single user.

Bring with you to the doctor, or use at home for:

- STINGS
- SPLINTERS
- SHOTS

BuzzyHelps.com

Home Use Rev. 02.01.17

ICE WINGS:

Wings will stay frozen 10 minutes at room temperature. For best pain relief, the Wings must be frozen solid to avoid absorbing vibration.

Face the blue or smooth side of the Wings toward the skin for more numbing power. If sensitive to cold, the soft side of the wings should face the skin.

Tip: For long procedures or for medications that burn or sting, prepare additional Wings.

Store folded Wings in freezer. Gel inside Wings is a non-toxic, safe, food-grade product that may deteriorate if not stored properly.

Note: To transport, place the Wings between the ColdToGo bag blue ice inserts (sold separately), or between 2 commercial cold packs (sold separately) to maintain frozen temperature.

COMFORT STRAP:

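### Buzzy I and Buzzy II are defined in opposite ways in different sections, so two of the four randomised arms are not uniquely identified

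*Combined protocol and SAP*

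**What the plan says.** Rationale and Purpose sets out to compare the standard spray with "three non-pharmacological pain control devices (Buzzy Bee I, Buzzy Bee II and Shot Blocker"), so the two Buzzy versions are separate study interventions.

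The descriptions of those two versions are:

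| Place | Buzzy I | Buzzy II |
|---|---|---|
| Study Design and Duration, Interventional Groups | "Buzzy I (vibrating only) # 26-50 (GREEN") | "Buzzy II (vibrating and ice wings) # 51-75 (BLUE") |
| Study Procedures, Visit 2, list of the four groups | "Buzzy I (*with ice pack-wings") | "Buzzy II (*without ice pack-wings") |
| Attachment II, heading | with wings | without wings |

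The Attachment II heading reads "Buzzy Bee I (*with ice pack-wings*) and Buzzy Bee II (*without ice pack-wings").

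The number and colour key appears only in Study Design and Duration. That section describes the envelope content as a coloured sticker and a number, and does not mention the device configuration. Under Visit 2, "The envelopes identifying the four group assignments will be coded by number and color", the child's draw determines the method, and the possible assignments "are listed below and are further detailed in Attachments" I to III. Data Collection includes the distraction method used but does not say whether this is entered as a label or as the actual configuration.

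**The concern.** A randomised trial has to define each arm in one way only. Here the same two labels carry exchanged meanings, and the exchange concerns the only feature by which the labels tell the arms apart.

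The protocol's own sequence can bring the two versions together. A child draws a green envelope. The key makes that Buzzy I, vibration only. The Visit 2 text then points to a group list and an attachment in which Buzzy I has ice wings. The protocol lists many co-investigators and three clinics, so a uniform reading cannot be taken for granted.

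Two kinds of error are possible:

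- **Mixed delivery.** Staff or sites follow different definitions. Each Buzzy arm then becomes a blend of the two configurations.
- **Mixed reporting.** Delivery is uniform, but the data file or the report takes its arm descriptions from the other section. Both arms are then credited to the wrong configuration.

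Either error affects the comparison of the two Buzzy arms and the comparison of each with ShotBlocker and with the spray. It also affects the attribution of adverse events, because Risk Assessment names skin irritation from the ice pack as a potential risk and events are judged against the assigned technique. Each child has one treatment session, so a configuration not recorded then may not be recoverable.

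**Working it through.** **Inputs from the documents** (Study Design and Duration): envelopes 1–25 ShotBlocker, 26–50 Buzzy I, 51–75 Buzzy II, 76–100 spray.

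**The plan's own figure.** Each range holds 25 envelopes (for example 50 − 26 + 1 = 25), and 4 × 25 = 100, as stated.

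**Exposed envelopes.** (50 − 26 + 1) + (75 − 51 + 1) = 25 + 25 = 50 of 100. The ShotBlocker and spray envelopes are not ambiguous.

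**Exposed comparisons.** Four arms give 4 × 3 / 2 = 6 pairs. Only ShotBlocker versus spray has no Buzzy arm, so 6 − 1 = 5 pairs are exposed.

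**Effect on the wings versus no-wings contrast.** Let V be the mean pain score under vibration only and W the mean under vibration plus wings. Let p1 be the share of the arm coded vibration only that in fact had wings, and p2 the share of the arm coded wings that in fact had none. The documents give neither share, so both are assumptions over 0 to 1. The swap is also assumed to be unrelated to the child's pain.

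- Arm coded vibration only: mean (1 − p1)V + p1·W
- Arm coded wings: mean (1 − p2)W + p2·V
- Difference, wings minus no wings: (1 − p1 − p2)(W − V)

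| Sessions swapped | p1 | p2 | Multiplier |
|---|---|---|---|
| None | 0 | 0 | 1 |
| 5 of 25 in one arm | 0.2 | 0 | 0.80 |
| 5 of 25 in each arm | 0.2 | 0.2 | 0.60 |
| 10 of 25 in each arm | 0.4 | 0.4 | 0.20 |
| All 25 in one arm only | 1 | 0 | 0 |
| All 25 in both arms | 1 | 1 | −1 |

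The sign reverses once p1 + p2 exceeds 1, that is, once the average swapped share exceeds 50%.

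**Effect on comparisons with ShotBlocker or spray.** The arm coded vibration only is shifted by p1(W − V), and the arm coded wings by −p2(W − V).

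**Could it be an ordering slip in a list?** No. Buzzy I is item 2 and Buzzy II item 3 in both group lists; only the descriptions are exchanged. All three places are current text.

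**The case against.** The strongest reply is that the key in Study Design and Duration is the only means of decoding an envelope, and it states the configuration beside each number and colour. Staff who work from that key alone would give one consistent device per colour. The Visit 2 list has no numbers or colours, so a swap needs a second step: green is read as Buzzy I, and Buzzy I is then looked up elsewhere. That is fair, and the documents do not show that a swap would happen. But the Visit 2 text does point the reader from the coded envelope to the list and attachments with the reversed definition. Consistent delivery also gives no protection against a report that describes the arms from the other section.

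Four further points stand as limits on the claim:

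- The swapped shares are unknown, so only the counts (50 of 100 envelopes, 5 of 6 pairs) come from the documents. The multipliers show a range and are not an estimate.
- A complete and uniform swap could be corrected by relabelling, once known. Information is lost when delivery is mixed and unrecorded.
- Data Analysis specifies no pairwise tests. The wings versus no-wings contrast is implied by the stated purpose, not defined in the plan.
- The Excel tool is not in the documents and may record the configuration. The text does not require it to, and the Attachment V worksheet has no device field.

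**Conclusion.** The concern holds, and the text must be corrected. The protocol gives opposite definitions for two of its four arms and no rule for choosing between them. This is more than a clerical slip, because it leaves open what the two arms are.

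The exposure is 50 of 100 envelopes and 5 of 6 pairwise comparisons. Fifty is an upper bound, reached only if every Buzzy participant is treated under one definition and coded or reported under the other. With one definition used throughout, the number misattributed is 0. In between, the contrast is diluted by 1 − p1 − p2 under the assumptions stated with the calculation. If the method is entered only as Buzzy I or Buzzy II, the data file cannot show which case occurred.

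**What to change.** 1. The sponsor reconciles Study Design and Duration, the Visit 2 group list and the Attachment II heading to one definition of its choosing. The documents do not establish which is intended.
2. State the configuration in words (vibration only; vibration plus ice wings) on the envelope key, in the procedures, in Attachment II and in the Excel tool, whether or not the I/II labels are kept.
3. Record whether wings were attached, yes or no, at delivery. This needs a separate post-assignment line or short form, because the Visit 2 procedures place the Attachment V interview before randomisation. The reconciled wording cures the contradiction; this entry makes any departure from it visible.
4. As a minor clarification, the leaflet in Attachment II suggests that children may choose whether to use the ice pack. The text should say how that is reconciled with randomised assignment.

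The cost of the main change is wording in three places, one yes/no entry and one spreadsheet column. No patients, visits or procedures are added.

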Our Comfort Strap is a reusable, single-handed tourniquet, smooth and pinch free. To use, 1. Loop the Comfort Strap around the arm, passing one end through the slit in the other. 2. Hold the slit and pull the other end through until the desired tension is reached, then release the slit end. 3. To lock the Comfort Strap in position, release the tension from the long end. 4. To release, simply pull gently on the short end and the Comfort Strap will fall away.

For shots: Switch on to activate the vibration, and then place Buzzy® on the site of the shot. Leave for 15 seconds for surface shots – 60 seconds for deeper injections. Immediately before cleaning the site, move Buzzy® proximal (closer to the head) to the pain location, and press in place throughout cleaning and getting the shot.

For children who get their shots sitting up, a parent can put an arm around the shoulders to hold Buzzy® for them.

INDICATIONS FOR USE	1
CONTRAINDICATIONS, WARNINGS, AND CAUTIONS	1
ICE WINGS	2
COMFORT STRAP	2
DIRECTIONS FOR USE	3
BUZZY PLACEMENT	4
SHOTS	5
STOMACH INJECTIONS	6
FOR ACHEs AND PAINS	6
FINGER STICKS, SPLINTERS	7
BURNING, ITCHING	7
IVs AND PHLEBOTOMY	8
CLEANING, CHANGING BATTERIES, TROUBLESHOOTING, ORDERING, GUARANTEE	10

DIRECTIONS FOR USE:

Immediately before use, remove the Wings from the freezer and attach behind Buzzy® on the hook. Activate by firmly pressing button on top of Buzzy®. Press a second time to turn Buzzy® off.

Buzzy® has an energy saving automatic shut-off after 3 minutes of constant use. Simply press the button on top of Buzzy® to reactivate vibration.

Buzzy comes with a silicone Comfort Strap to hold Buzzy in place on extremities. 1. Loop the Comfort Strap around the arm, passing one end through the slit in the other. 2. Hold the slit and pull the other end through until the desired tension is reached, then release the slit end. 3. To lock the Comfort Strap in position, release the tension from the long end. 4. To release, simply pull gently on the short end and the Comfort Strap will fall away.

Use Buzzy® only on clean, unbroken skin. The stripes on Buzzy®, or bottom end should be closest to the procedure, and the head on Buzzy® and switch farthest away.

Tip: For best results, center the bigger rounded end of Buzzy® directly next to the pain.

INDICATIONS FOR USE:

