Face 0 doesn't hurt at all. Face 2 hurts just a little bit. Face 4 hurts a little bit more. Face 6 hurts even more. Face 8 hurt a whole lot. Face 10 hurts as much as you can imagine, although you don't have to be crying to have this worst pain.

Ask the person to choose the face that best depicts the pain they are experiencing.

Numeric Rating Scale

PAIN SCORE 0-10 NUMERICAL RATING

0-10 Numerical Rating Scale

0 1 2 3 4 5 6 7 8 9 10

No Pain Moderate Pain Worst Possible Pain

Instructions: Parent/ Guardian, please circle what pain level YOU percieve YOUR child to be in just after receiving their subcutaneous Immunotherapy (allergy shots).

PPAST v1.0-Numeric Rating Scale

V – Parent Questionnaire: Demographic – Health – Treatment Questionnaire

PPAST study Source Document Worksheet – Attachment V
PI: [name], MSN, APRN, PCNS-BC, CPEN

Participant ID: _____ Visit 2: ____/____/____

Demographic – Health – Treatment Questionnaire: Parent Interview

*Investigator will interview the parent to complete this questionnaire.
Questionnaire to be completed prior to administering allergy shot.*

1. How old is your child? _____
2. What race / ethnicity is your child? _____
3. What gender is your child? _____
4. How long has your child been on allergy shots? (Estimate in weeks, months or years) _____
5. What is the number of allergy shots your child will receive today? _____
6. What color vial is your child on? _____
7. What is your child's dose for the allergy shot? _____
8. What kind of allergy shot is your child receiving – venom / fire ant / environment? _____
9. Has your child ever had symptoms after receiving allergy shots? _____
If yes, explain: _____

10. Has your child taken any medication for pain today? _____
If yes: What was the name and dose of the pain medication? _____
For what reason was the medication given? _____
What time was the medication given? _____
11. Does your child use antihistamine medications? _____
If yes: What was the name and dose of this medication? _____
How often is the medication given? _____
What time was the medication given? _____
11. Please check the if your child has any of the following symptoms:

Allergic Rhinitis Asthma Atopic Dermatitis

Investigator Signature _____ : _____
Time form completed _____ / _____ / _____
Date form completed

V1.0 – 15Dec18

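### A single pain rating follows one injection in some children and several in others: state that it comes after the last injection, and adjust for the recorded number of injections

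*Combined protocol and SAP*

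**What the plan says.** Under *Study Procedures, Visit 2*, the plan expects some children to have several injections: "If the child's treatment plan includes more than one injection, the assigned group technique will be utilized for all injections at the visit". Attachment V, item 5, asks the parent for the count: "What is the number of allergy shots your child will receive today".

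There is one post-injection rating from each rater. For the child, *Post allergy injection procedures* says: "Immediately following the allergy injection, the child will be provided with a second Wong-Baker FACES Pain Rating Scale form". The child is then "asked to circle the face which most closely matches their post-injection level of pain awareness". The parent's numeric form in Attachment IV asks for the pain perceived "just after receiving their subcutaneous Immunotherapy (allergy shots", which is plural. The parent's step in *Post allergy injection procedures* uses the singular, as the child's does.

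No text says whether the rating follows the first or the last injection, or whether it covers worst or overall pain. The *Data Analysis* section lists diagnoses, medication and dose, other medicines, pain scores, adverse reactions and demographics. The number of injections is not named there, and no stratification or adjustment for it is described.

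**The concern.** Pain perception is what this trial is about, although no outcome is labeled primary. If one child is rated after a single needle and another after three, their scores are not quite the same quantity. That spread has nothing to do with the technique. It widens the variance in every arm and, in small arms, can fall unevenly by chance. The plan collects the variable that would remove most of this and then does not mention using it.

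The wording gap adds a second, smaller problem. Staff at three clinic locations must each interpret the child's step, and the singular and plural wordings allow child and parent to rate different events at the same visit. As reproduced, neither pain scale has a field for the time of rating or the injection rated, so a departure could not be detected afterwards.

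**Working it through.** **1. Which moment do the documents imply?** Visit 2 is laid out in three stages: before applying the method, application and injection, and post-injection procedures. The second stage covers all injections of the visit. The rating opens the third, and the routine 30-minute wait follows it. The parent form is plural. Together these point to a rating after the last injection, but the child's step does not state it. I take after the last injection as the natural reading.

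**2. Is the number of injections a baseline characteristic?** Yes. It comes from the treatment plan, and the procedures place the parent interview before randomization. Allocation cannot influence it, so it is balanced in expectation and is a legitimate covariate.

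**3. The plan's own figure.** 4 groups × 25 envelopes = 100, as stated. The plan gives no SD, effect size or power, so nothing further can be reproduced. The inputs below, other than 25 per arm, are assumptions for scale only:

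- share of children with more than one injection: p = 0.3, 0.5, 0.7
- shift in score when more than one injection is given: s = 1 or 2 points
- SD among children with the same number of injections: 2.5 points
- difference between two arms to be detected: 2 points, two-sided 0.05

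The number of injections is simplified to one versus more than one.

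**4. Chance imbalance between two given arms.** Let X₁ and X₂ be independent Binomial(25, p). A gap of 20 percentage points is 5 children out of 25.

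- P(|X₁ − X₂| ≥ 5) = 0.164 at p = 0.3, 0.203 at p = 0.5 and 0.164 at p = 0.7.
- Effect of a 20-point gap on the arm difference: 0.20 × 1 = 0.2 points; 0.20 × 2 = 0.4 points.

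**5. Added variance and power.** Unadjusted SD = √(2.5² + p(1 − p)s²). Power = Φ(2 / (SD × √(2/25)) − 1.96).

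| s | p | SD | power |
|---|---|---|---|
| 0 | any | 2.50 | 0.807 |
| 1 | 0.3 | 2.54 | 0.794 |
| 1 | 0.5 | 2.55 | 0.792 |
| 2 | 0.3 | 2.66 | 0.757 |
| 2 | 0.5 | 2.69 | 0.747 |

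Because p(1 − p) is the same at 0.3 and 0.7, the p = 0.3 rows also serve for 0.7. The loss ranges from 0.807 − 0.794 = 0.013 to 0.807 − 0.747 = 0.060. Steps 4 and 5 describe the same source of error, once for a particular draw and once averaged over draws, so they should not be added together. Under these assumptions, adjusting for the number of injections takes the SD back to about 2.5.

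**The case against.** The best defense is that the plan already implies a rating after all injections. The steps are in that order, the parent form is plural, and the protocol elsewhere uses the singular generically, including in the heading of the stage where one or more injections are given. On that reading staff have no choice to make, the number of injections is balanced in expectation, and only some noise remains. Most of this stands. It reduces the wording issue to a clarification. It does not answer the analysis gap: under exactly that reading the scores mix different numbers of needles, and the recorded count is unused.

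A reader might go further and infer that the timing of the rating differs systematically by arm. The investigator applies the method and gives the injection, so the arm is known, and the attached instructions differ: for one device, "After you have completed the injection and withdrawn the needle, remove and discard ShotBlocker"; for the other, "press in place throughout cleaning and getting the shot". The documents do not support that inference. Both instructions describe a single injection. The ShotBlocker attachment also says that one device per patient is enough. The Buzzy instructions have the device left on the site for 15 to 60 seconds and then moved before cleaning, so repeated use would involve a pause there too. No text gives an interval between injections or links handing over the form to removing a device. Timing may differ by arm if staff hand over the form at different moments. Nothing shows that it will, and no figure for such a bias can be derived from the documents.

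**Conclusion.** The point holds as a gap in outcome definition and a missed covariate; a systematic bias between arms is not shown. With 25 children per arm and the assumed inputs, two given arms have roughly a one-in-six to one-in-five chance of differing by 20 percentage points or more in the share with several injections. An imbalance of exactly 20 points moves their difference by 0.2 to 0.4 points, or 10% to 20% of a 2-point effect. Power falls by about 1 to 6 percentage points. If nearly all children have the same number of injections, or if further injections do not change the rating, the loss is close to zero. This does not threaten the validity of the trial, but the improvement costs almost nothing because the variable is already collected.

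**What to change.** Make two changes.

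1. In *Study Procedures, Visit 2*, and on both pain forms, state that the child's FACES rating and the parent's numeric rating are each completed once, immediately after the last injection of the visit, for every child in every arm. Use the same wording for both raters. This matches the existing order of steps and adds no pause between injections.
2. In *Data Analysis*, name the number of injections (Attachment V, item 5) and include it as a prespecified covariate in the between-group comparison of pain scores. The section attaches its significance level to demographic characteristics and describes no such comparison, so the sentence should say that the covariate belongs to the pain-score model.

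The cost is two sentences and a wording change on the forms, plus slightly more analysis work than simple Excel functions, since the comparison becomes a regression with arm and number of injections. No extra data collection is needed.
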